range, the current treatment will be continued; 50% > hrds-17 score reduction rate > 30% or the drug concentration is lower than the minimum recommended concentration, the current treatment can be continued or the dose can be adjusted; If the score reduction rate of hrds-17 is less than 30% and the drug concentration is lower than the minimum value of the recommended concentration, the dosage should be adjusted. If the score reduction rate of hrds-17 is less than 30% and the drug concentration is higher than the minimum value of the recommended concentration, the dressing should be changed. If intolerable side effects occur, the dose can be reduced, or the dressing can be changed.

Design method of cognitive training program

Intervention implementation plan

The total duration of this intervention was 52 weeks, during which training tasks were carried out in weeks, and patients were arranged to carry out cognitive training in different fields. During the intervention period, patients need to complete a total of 52 weeks of training plan, including 4 training days per week (it is recommended to ensure the frequency of every other day). Each training day includes at least 3 different cognitive training. The duration of each training is about 60min, and the total duration of each month shall not be less than 16 hours.

Intervention scheme generation rules

The cognitive training program will push personalized cognitive training according to the performance of the subjects in the six areas of episodic memory, executive function, working memory, processing speed, speech ability and reasoning judgment. Patients need to be evaluated once a month and update the training program according to the evaluation performance.

The specific recommendation principles of the training program in the intervention group are as follows: the areas with poor cognitive performance (1.5 standard deviations lower than the average value of the norm) are recommended first, and more than one and no more than four times in each training cycle; Secondly, recommend areas with poor cognitive performance (1 standard deviation lower than the norm), and

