Exclusion criteria: 1.patients with history of epilepsy or coronary heart disease or other serious unstable physical diseases; 2. Participated in another intervention clinical study in the past 1 month; 3. The following mental diseases have been or are currently diagnosed by DSM-V: organic mental disorder, Alzheimer's disease, secondary dementia caused by other causes, schizophrenia, schizophrenic affective disorder, bipolar disorder, delusional disorder, undefined mental disease, patients with drug abuse history, including alcohol and active drug abuse in the past 12 months, except nicotine; 4.He has been taking antidepressants, mental retardants and other psychiatric drugs for the past 2 weeks; 5. Severe aphasia, visual and hearing impairment, etc. unable to complete the scale evaluation; 6. Pregnant, lactating women or those planning to conceive.

The subject may withdraw from the study for any of the following reasons: the investigator considers that it is best for the subject to terminate the treatment due to safety factors (such as adverse events); The subjects were lost to follow-up; The subject withdrew informed consent. If a subject is lost to follow-up, the staff of the research center shall make every effort to contact the subject and determine the reason for his withdrawal. Follow up examinations must be recorded. When a subject withdraws before completing the study, the reason, date, and final evaluation of withdrawal shall be recorded in the CRF and original documents.

Symptomatic assessment

1) Hamilton Anxiety Rating Scale (HAMA): in the baseline period, at the end of the 2nd, 4th, 8th, 12th, 26th, 38th and 52nd weeks, the rater assessed the anxiety symptoms of the subjects.

2) The Hamilton Rating Scale for depression (hrsd-17): subjects were assessed for depressive symptoms at the end of the baseline period, 2 weekends, 4 weekends, 8 weekends, 12 weekends, 26 weekends, 38 weekends and 52 weekends.

3) The Geriatric Depression Scale (GDS): subjects were evaluated for depressive symptoms at the end of the baseline period, 2 weeks, 4 weeks, 8 weeks, 12 weeks, 26 weeks, 38 weeks, and 52 weeks.

4) Neuropsychiatric Inventory (NPI): subjects were assessed for cognitive function at the end of the baseline period, 2 weeks, 4 weeks, 8 weeks, 12 weeks, 26 weeks, 38 weeks, and 52 weeks.

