8. Effective rate of treatment: the proportion difference between the two groups of subjects in the reduction rate of hrds-17 scale at each visit point and the baseline $\geq 50\%$.

9. Recurrence rate and recurrence time: recurrence is defined as any of the following conditions: the subject meets the DSM-IV diagnostic criteria for depressive episode; The subject was hospitalized again due to depression; After the treatment was effective (ham-d17 score decreased by $\geq 50\%$ compared with the baseline), ham-d17 score increased by more than 30% compared with the baseline at any visit point; During the maintenance treatment period, after the treatment of the subjects is effective or remission, the proportion of relapse and the time of relapse between the two groups at each visit point;

Safety index:

i. Abnormal values of vital signs, laboratory examination and electrocardiogram examination during the study period.

II. Adverse events and adverse reaction reports during the study period.

Basis for determining sample size

According to the main research hypothesis of this study, the effect of comprehensive intervention group on improving patients' cognition is better than that of conventional treatment group. According to the previous similar research results and the expected efficacy hypothesis, the difference between the groups of the study group and the control group in terms of ADAS cog score reduction after 12 weeks of treatment is about 2.2, and the combined standard deviation is 4. Set $\alpha = 0.025$ (one side), $\beta = 0.20$, and set the superiority and effectiveness limit value as 3 in combination with the

previous research and clinical significance, The ratio of the number of cases in the study group to the control group was 1:1. The sample size of the study group was 51 cases, and the sample size of the control group was 51 cases. Considering the 20% rejection rate of similar items, 64 cases need to be included in the study group and the control group.

Statistical analysis methods

Full Analysis Set (FAS): A collection of all randomized cases with valid baseline assessments. FAS is the main analysis set. Secondary efficacy measures were analyzed using only FAS without carry-over.

General principles: Statistical analysis was performed using SAS.9.4 statistical analysis software. P value < 0.05 was statistically significant (unless otherwise specified).

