Statistical description: Measurement data are described using mean (standard deviation), median (interquartile range), minimum value, and maximum value; skewed distribution indicators are normally corrected before analysis, unless otherwise specified. Enumeration data were described using the number of cases (percentage).

Statistical analysis methods

Full Analysis Set (FAS): A collection of all randomized cases with valid baseline assessments. FAS is the main analysis set. Secondary efficacy measures were analyzed using only FAS without carry-over.

General principles: Statistical analysis was performed using SAS.9.4 statistical analysis software. A P value < 0.05 was statistically significant (unless otherwise specified).

Statistical description: Measurement data are described using mean (standard deviation), median (interquartile range), minimum value, and maximum value; skewed distribution indicators are normally corrected before analysis, unless otherwise specified. Enumeration data were described using the number of cases (percentage).

1) Efficacy analysis:

Primary Endpoint Analysis

The between-group difference in the change from baseline in the total score of the two groups of subjects (ADAS-cog) at the end of 12 weeks

Statistical analysis of changes from baseline in ADAS-cog total scores at the end of 12 weeks was performed using MMRM (mixed model for repeated measures). The model takes the change of ADAS-cog total score at each time point after treatment relative to the baseline as the dependent variable, the baseline ADAS-cog total score is a covariate, and the grouping is a fixed effect. Each fixed effect factor and covariate is nested in each visit. Inside. According to the model, the adjusted mean of the total ADAS-cog total score at the end of treatment in each group compared with the baseline, as well as the difference of the adjusted mean between the two groups and its 95% confidence interval, the lower limit of the confidence interval and the set optimal value were calculated. The comparison of the effect-media value was used as the criterion for superiority.

Secondary endpoint analysis:

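### The withdrawal rule does not separate stopping treatment from leaving the study, so week-12 ADAS-cog may be lost for participants whose treatment is stopped for safety

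*Combined protocol and SAP*

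**What the plan says.** All references are to the combined protocol and SAP.

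- **Research object, withdrawal paragraph after the exclusion criteria.** The list opens with "The subject may withdraw from the study for any of the following reasons". The first reason is that "the investigator considers that it is best for the subject to terminate the treatment due to safety factors". The other two are loss to follow-up and withdrawal of consent. For anyone who leaves early, "the reason, date, and final evaluation of withdrawal shall be recorded in the CRF and original documents". Between these, directly after the instruction to try to contact subjects lost to follow-up, a short sentence says that follow-up examinations must be recorded.
- **Drug therapy intervention.** Short of termination, the plan allows treatment to be adjusted: "If intolerable side effects occur, the dose can be reduced, or the dressing can be changed".
- **Efficacy index.** The primary endpoint is change in ADAS-cog at week 12. Change at every other follow-up point is secondary, and the study runs to week 52.
- **Statistical analysis methods.** The full analysis set (FAS) is "A collection of all randomized cases with valid baseline assessments. FAS is the main analysis set". The primary analysis "was performed using MMRM (mixed model for repeated measures)", with baseline score and group as terms at each visit. No estimand, missing-data assumption, rule for treatment discontinuation or sensitivity analysis is given. The only related wording, that nothing is carried over, concerns secondary measures.

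**The concern.** A decision about treatment appears in the same list as two events that really do end observation. A site following the paragraph could close a participant's record when treatment is stopped for safety, although that participant may be willing and able to attend the remaining visits. No other section says that stopping treatment and leaving the study are different, or asks for ADAS-cog after treatment stops.

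The analysis set points the other way: it keeps everyone randomised with a valid baseline. A participant withdrawn in week 5, for example, stays in the FAS but has no week-12 value. One withdrawn before any post-baseline ADAS-cog contributes no outcome to a change-score model at all.

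People stopped for safety are unlikely to be a random subset. If their later course differs from that of similar arm-mates who stayed, the week-12 estimate does not describe the whole randomised population. Values that were never collected cannot be recovered at analysis, so this has to be settled in the protocol.

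**Working it through.** **Inputs from Basis for determining sample size:** difference 2.2 points, SD 4, one-sided alpha 0.025, beta 0.20, 1:1 allocation, 51 per arm evaluable, 20% loss, 64 per arm enrolled. The causes of the 20% are not split.

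**Reproducing the plan's figure.** n per arm = 2 × [4 × (1.960 + 0.842) / 2.2]² = 51.9, which rounds up to 52 against the stated 51. Power at 51 is 79.3%. Allowing for loss, 51 / 0.80 = 63.75, or 64, as stated. The superiority limit of 3 plays no part in this arithmetic and is not needed here.

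**Effect in all randomised patients.** These assumptions are not in the documents:
- a share s of the training arm stops for safety before week 12;
- stoppers keep a fraction r of the 2.2-point effect;
- nothing comparable happens in the control arm;
- stoppers' earlier scores give no sign of what follows, so a missing-at-random analysis still targets about 2.2.

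All-randomised effect = 2.2 × [1 − s(1 − r)]. Overstatement = 2.2 × s(1 − r).

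| s | Effect, r = 0 | Overstatement, r = 0 | Overstatement, r = 0.5 |
|---|---|---|---|
| 2% | 2.16 | 0.04 | 0.02 |
| 5% | 2.09 | 0.11 | 0.06 |
| 10% | 1.98 | 0.22 | 0.11 |
| 20% | 1.76 | 0.44 | 0.22 |

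The 20% row is a ceiling on the plan's own allowance: every lost participant would be a safety stop before week 12. For scale, the planned SE is 4 × √(2/51) = 0.79, so 0.02 to 0.44 points is about 3% to 56% of one SE.

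**Stops in both arms.** Let L be the improvement that stoppers lose relative to those who stay, with T for training and C for control. The overstatement becomes s_T × L_T − s_C × L_C. It is zero when the two products are equal and negative when the control product is larger.

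**Effect on power of following stoppers.** Power = Φ(effect / SE − 1.96), with s = 10% and r = 0:
- As planned: 2.2 / 0.792 = 2.78, power about 79%.
- 57 per arm followed (about half of the 13 otherwise lost are kept, 51 + 6): SE = 4 × √(2/57) = 0.749; 1.98 / 0.749 = 2.64, power about 75%.
- All 64 per arm followed: SE = 4 × √(2/64) = 0.707; 1.98 / 0.707 = 2.80, power about 80%.

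At s = 20% and r = 0 with all 64 followed, 1.76 / 0.707 = 2.49 and power is about 70%.

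**The case against.** **The wording is permissive.** A reader might infer that every safety stop must end ADAS-cog follow-up. The text does not say so: a subject *may* withdraw, and later visits are not barred. The sentence on recording follow-up examinations could be read as asking for them, but it follows the loss-to-follow-up instruction and does not clearly require visits after a safety stop. What stands is a missing distinction and a missing provision, not a prohibition.

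**The trigger is narrow.** It needs an investigator's judgement that ending treatment is best for safety. Side effects can be handled by adjustment, and skipping training is not one of the three listed reasons, so non-adherent participants have no listed reason to leave. This limits how many are affected. It does not help those who are withdrawn.

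**The MMRM is not blind to stoppers.** A reader might infer that it treats them as if they had stayed on treatment. It does not do so literally. It uses their own earlier ADAS-cog changes and arm-mates who stayed, some of whom may have changed drug or trained little. A decline seen before stopping enters the estimate; a change after stopping does not.

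**The direction is not established.** Both arms receive SSRIs, so safety stops can occur in both. The plan's own rationale holds that SSRIs do not significantly improve cognition in these patients and may worsen it, so stopping one need not worsen ADAS-cog. This objection stands.

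**The FAS definition does not by itself fix an estimand.** That is true, and the plan names none. But whichever effect is chosen, one that covers all randomised patients needs outcomes after treatment stops.

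**Conclusion.** The concern holds in a limited form. The plan does not distinguish stopping treatment from leaving the study, and following its withdrawal paragraph can lose week-12 ADAS-cog in participants whom the main analysis set retains. The MMRM then depends on an unstated missing-at-random assumption, which *could* bias the effect in all randomised patients.

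The size is unknown. The illustrative range of 0.02 to 0.44 points rests on an assumed stopping share, stops in the training arm only, half or none of the benefit kept, and uninformative earlier scores. A reader might take the upper rows as the expected result, an overstatement of 11% (0.22 / 1.98) or 25% (0.44 / 1.76). The documents do not support that: they give no rate of safety stops, and those rows assume that half or all of the loss allowance is safety stopping before week 12 with the whole benefit gone.

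Only stops before week 12 bear directly on the primary endpoint. Later ones affect the secondary comparisons to week 52. The change is worth making because it is cheap and the lost data cannot be recovered.

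**What to change.** 1. In the withdrawal paragraph and the CRF, record *stopped study treatment* (SSRI, training or both, with date and reason) separately from *left the study*.
2. State that participants who stop the SSRI or the training stay on the existing visit schedule for ADAS-cog and the other scales through week 12, and to week 52 where they agree, unless they withdraw consent or are lost.
3. State that these data are included in the FAS MMRM.

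The cost is wording and a CRF field, using visits already planned. The downside is dilution. In the 10% example with no benefit kept, power is about 75% with 57 per arm followed and about 80% with all 64, against about 79% as planned; more stopping would lower it further. The sponsor should accept that knowingly. Nothing here changes when or why treatment is stopped.

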no more than 2 times in each training cycle; In addition to the above fixed training, if the training content does not reach 16 items / week, cognitive training in other fields will be randomly pushed; Within each training day, only one cognitive rehabilitation training is arranged for each cognitive field; The difficulty of each cognitive rehabilitation training depends on the last training level of the subject.

Training scheme of the control group: to keep the same electronic use time as that of the intervention group, the subjects in the control group are required to open the electronic products for 60 minutes every day, 4 days a week.

Intervention mode

Tablet computer or mobile phone to be used in this intervention training. The training will take the principles of psychology and cognitive neuroscience as the core, and interactive games as the carrier, covering the cognitive training in six fields: episodic memory, executive function, working memory, processing speed, speech ability and reasoning judgment, to ensure the scientific on the premise of enhancing interest.

According to their own conditions, the subjects can choose to go to the hospital to use the tablet computer provided by the hospital for training within the reserved time or can use their own tablet computer or mobile phone for independent training. The training mode of this intervention is flexible. The subjects can start training on different terminal devices, and the training records can also be updated in real time. The research team will monitor the whole training process.

Research object

Inclusion criteria: 1. written informed consent signed by patients and their families; 2. Age ≥ 60 years; 3. Meet the diagnostic criteria for single or recurrent major depressive disorder in the diagnostic and Statistical Manual of mental disorders Fourth Edition (DSM-V); 4. Currently in the acute phase, the total score of hrds-17 at baseline is ≥ 18 points. 5. There were cognitive impairment symptoms, and the Montreal Cognitive Assessment Scale (MoCA) was < 26 points. 6/ Education level above primary school.

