5) Activities of daily living (ADL): the cognitive function of the subjects was assessed in the baseline period, 2 weekends, 4 weekends, 8 weekends, 12 weekends, 26 weekends, 38 weekends and 52 weekends.

Safety evaluation

1) Vital signs: the temperature, pulse and blood pressure of the subjects were monitored at the end of the baseline period, 2 weekends, 4 weekends, 8 weekends, 12 weekends, 26 weekends, 38 weekends and 52 weekends.

2) Adverse event report: adverse event records were made on the subjects at the end of the baseline period, the end of the 2nd week, the end of the 4th week, the end of the 8th week, the end of the 12th week, the end of the 26th week, the end of the 38th week and the end of the 52nd week.

3) Treatment Emergent Symptom Scale (TESS): during the baseline period, the subjects were evaluated for side effects at the end of 2 weeks, 4 weeks, 8 weeks, 12 weeks, 26 weeks, 38 weeks, and 52 weeks.

4) Laboratory examination and electrocardiogram: routine blood test, biochemical examination and electrocardiogram examination were conducted at the end of the

screening period, the end of the 4th week, the end of the 12th week, the end of the 38th week and the end of the 52nd week.

Efficacy index

1) Main efficacy indicators:

At the end of the 12th week after treatment, the change value of ADAS cog scale scores of the subjects in the two groups compared with the baseline.

2) Secondary efficacy indicators:

1. At each follow-up point, the change value of ADAS cog scale scores of the two groups compared with the baseline.

2. At each follow-up point, the change value of hrsd-17 score of the subjects in the two groups compared with the baseline;

3. At each follow-up point, the change value of HAMA scale scores of the two groups compared with the baseline.

4. At each follow-up point, the change value of GDS score of the subjects in the two groups compared with the baseline.

5. At each follow-up point, the change value of NPI scale scores of the subjects in the two groups compared with the baseline.

6. At each follow-up point, the change value of ADL scale scores of the subjects in the two groups compared with the baseline.

7. Complete remission rate: the difference in the proportion of patients with a total score of hrds-17 ≤ 7 at each visit point between the two groups.

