Efficacy evaluation indicators include HRSD-17, HAMA, GDS, NPI, ADL and other scales. The differences between groups at the visit point relative to the baseline value were analyzed using the same analysis method as the main efficacy indicators. The cumulative complete remission rate, treatment response rate, recurrence rate and other outcome indicators during the study period were compared between groups using the Kaplan-Meier curve, and the COX proportional hazards model was used to evaluate the impact of the intervention while controlling for confounding factors such as disease duration.

Safety analysis: The incidence of adverse events and adverse reactions was tested by chi-square and described in a list.

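### Recurrence criterion 1 can count a partial responder whose index depressive episode never ended as a recurrence, with no worsening

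*Combined protocol and SAP*

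**What the plan says.** The recurrence endpoint is item 9 of the secondary efficacy indicators (Efficacy index section). It lists alternative conditions, any one of which is enough: "recurrence is defined as any of the following conditions: the subject meets the DSM-IV diagnostic criteria for depressive episode"; readmission for depression; or, once a patient has responded, a rise of more than 30% in the HAM-D17 score. Only the score condition carries a prior-response requirement in its own wording.

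The item closes with a clause on what is compared: "During the maintenance treatment period, after the treatment of the subjects is effective or remission, the proportion of relapse and the time of relapse", between groups at each visit.

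Item 8 defines an effective treatment as an HRSD-17 reduction of at least 50% from baseline. Item 7 defines remission: "Complete remission rate: the difference in the proportion of patients with a total score of hrds-17 ≤ 7 at each visit point".

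At entry, patients must "Meet the diagnostic criteria for single or recurrent major depressive disorder" and satisfy "Currently in the acute phase, the total score of hrds-17 at baseline is ≥ 18 points".

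Under secondary endpoint analysis, "recurrence rate and other outcome indicators during the study period were compared between groups using the Kaplan-Meier curve", with a Cox model for the intervention effect. That section gives no risk set and no time origin. The maintenance treatment period is not defined anywhere, and secondary measures are analysed in the FAS, which is all randomised cases with a valid baseline.

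**The concern.** A recurrence is a change: the patient leaves the episode and later returns to one. Criterion 1 asks only whether episode criteria are met. It requires neither a visit at which they were not met nor any worsening. Since all patients enter the trial in an episode, the criterion cannot by itself tell a new episode from the old one.

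The closing clause screens out patients who have not improved. It does not screen out those who improved by half and are still ill, because it admits response as an alternative to remission. For them the recurrence endpoint would record incomplete recovery as relapse. If this happens equally in both arms, the comparison is pulled towards no difference. If one arm has more partial responders, a recurrence difference can appear that has nothing to do with relapse prevention.

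**Working it through.** The plan gives no recurrence rate, event count or power for this endpoint, so there is no stated figure to reproduce. The check sets the definitions side by side and then shows how sensitive the comparison is.

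**Step 1. Is there a gap between response and remission?** Response is HRSD-17 ≤ 0.5 × baseline (item 8); remission is HRSD-17 ≤ 7 (item 7); entry needs a score of at least 18 (inclusion item 4). Baselines above 18 are illustrative.

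| Baseline | Response at or below | Responder but not in remission |
|---|---|---|
| 18 | 9 | 8 to 9 |
| 24 | 12 | 8 to 12 |
| 28 | 14 | 8 to 14 |
| 30 | 15 | 8 to 15 |

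The gap exists at every permitted baseline and widens with severity. A patient going from 28 to 14 is counted as effectively treated at twice the remission threshold.

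**Step 2. Follow such a patient through item 9.** The fall to 14 satisfies the effective limb of the closing clause, so relapse counting opens. At a later visit the score is still 14 and the clinician judges that episode criteria are still met. Criterion 1 is satisfied and one condition is enough. A recurrence is recorded although the score has not moved and the index episode never ended.

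**Step 3. Does the analysis section prevent it?** No. It refers to the study period without restating the response/remission condition, and it gives neither a risk set nor a time origin.

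**Step 4. How many responders could be affected?** No document links an HRSD-17 score to meeting episode criteria, so any figure is an assumption. Assume baseline N(23, 4) truncated at 18, a gradual fall to an individual plateau, visit noise SD about 2, and a logistic chance of still meeting criteria. The share of responders still meeting criteria at their first response visit is then:

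- 12% to 54%, with the logistic midpoint between 15 and 11;
- about 3% to 4%, with the midpoint at 17 to 18, near the trial's own entry cut-off.

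These shares describe the first response visit. The closing clause counts events after response, so they indicate how many patients are exposed to the problem; they are not predicted event rates.

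**Step 5. Effect on the comparison (arithmetic only).** Let p be the true recurrence proportion among responders and f the fraction falsely counted, equal in both arms. Recorded proportion = f + (1 − f)p. Assume p = 0.30 in control and 0.18 in intervention, a true ratio of 0.18/0.30 = 0.60.

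| f | Control | Intervention | Ratio | False share of control events (f ÷ control) |
|---|---|---|---|---|
| 0.03 | 0.321 | 0.205 | 0.64 | 9% |
| 0.10 | 0.370 | 0.262 | 0.71 | 27% |
| 0.20 | 0.440 | 0.344 | 0.78 | 45% |
| 0.30 | 0.510 | 0.426 | 0.84 | 59% |

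For f = 0.10: control 0.10 + 0.90 × 0.30 = 0.370; intervention 0.10 + 0.90 × 0.18 = 0.262; ratio 0.262/0.370 = 0.71.

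**The case against.** The strongest defence is that the closing clause already supplies the missing condition. It places relapse in a maintenance phase that follows response or remission, and the readmission criterion also suggests that a return of illness was meant. This stands in part. A reader might infer from criterion 1 alone that everyone still depressed at week 2 is a recurrence, or that every unresolved episode is counted. The documents do not support that: a patient who has neither responded nor remitted falls outside the clause. Nor does the clause make the response visit itself the event, since it counts relapse after that visit. What the clause does not do is separate responders who have left the index episode from those who have not.

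A second objection is that the visit schedule lists rating scales and no repeat DSM assessment, so criterion 1 would rest on a clinician's diagnosis, and a sensible clinician would not call a persisting episode a recurrence. That could keep the number small. It also means the endpoint depends on unwritten judgement, because the written rule asks only whether criteria are met.

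A third is that the size depends wholly on assumption. This is correct: the share can be a few percent, and the 30% versus 18% illustration comes from no document.

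**Conclusion.** The point holds for responders who are not in remission. Followed as written, item 9 lets a persisting index episode count as a recurrence without deterioration, and nothing in the analysis section stops it. The recurrence proportion, Kaplan-Meier curve and Cox estimate could therefore mix incomplete response with relapse.

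The size cannot be fixed from the documents. Under the assumptions tried, it runs from about 3% to about half of responders, depending almost entirely on the score at which a patient is taken still to meet episode criteria. Equal misclassification dilutes a true difference; unequal misclassification can create a false one.

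This concerns one secondary endpoint. The ADAS-cog primary endpoint at week 12 and the sample size do not depend on it. It should be corrected because the rule as stated gives a wrong result for an identifiable group of patients and the correction is short.

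**What to change.** Reword criterion 1 in item 9 along these lines: after response or remission, and after at least one visit at which the index episode had ended (HRSD-17 ≤ 7, the plan's own remission definition, or depressive-episode criteria documented as not met), the subject again meets criteria for a depressive episode.

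Attach the response/remission condition of the closing clause explicitly to all the criteria, and repeat it in the secondary endpoint analysis as the definition of the risk set. Start time to recurrence at the visit where that condition is first met. Leave the readmission criterion otherwise unchanged, so that a responder who deteriorates and is admitted still counts.

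The cost is a sentence or two in item 9 and the matching derivation. HRSD-17 is already collected at every visit, so the remission route needs no new data; the alternative route needs episode status to be documented. The small downside is fewer recorded criterion-1 events, because a responder who never leaves the index episode can no longer have one.
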